8.2.6. Suicidal Ideation and Behavior Risk Monitoring

Participants who have obesity or are overweight are at increased risk for depression (Luppino et al. 2010). Depression can increase the risk for suicidal ideation and behavior. Therefore, study participants will be screened at trial entry and monitored during the study for depression, suicidal ideation, and behavior.

Participants should be monitored appropriately for suicidal ideation and behavior or any other unusual changes in behavior, especially at the beginning and end of the course of treatment, or at the time of dose changes, either increases or decreases. Consideration should be given to discontinuing the study medication in participants who experience signs of suicidal ideation or behavior, following a risk assessment.

Columbia Suicide-Severity Rating Scale (C-SSRS) is a scale that captures the occurrence, severity, and frequency of suicidal ideation and behavior during the assessment period via a questionnaire. The scale was developed by the National Institute of Mental Health (NIMH) trial group (TASA) for the purpose of being counterpart to the Columbia Classification Algorithm of Suicide Assessment (C-CASA) categorization of suicidal events.

Baseline and treatment-emergent assessment of depression, suicidal ideation, and behavior will be monitored during the study using the C-SSRS and PHQ-9 (Section 8.3.2.13).

8.3. Adverse Events, Serious Adverse Events, and Product Complaints

The definitions of the following events can be found in Section 10.4 (Appendix 4):

- AEs
- SAEs, and
- Product complaints (PCs).

These events will be reported by the participant (or, when appropriate, by a caregiver, surrogate, or the participant's legally authorized representative).

The investigator and any qualified designees are responsible for detecting, documenting, and recording events that meet these definitions and remain responsible for following up events that are serious, considered related to the study drug or study procedures, or that caused the participant to discontinue the study drug (see Section 7).

Care will be taken not to introduce bias when detecting events. Open-ended and non-leading verbal questioning of the participant is the preferred method to inquire about event occurrences.

After the initial report, the investigator is required to proactively follow each participant at subsequent visits/contacts. All SAEs and AEs of special interest (as defined in Section 8.3.2) will be followed until resolution, stabilization, the event is otherwise explained, or the participant is lost to follow-up (as defined in Section 7.3). For product complaints, the investigator is responsible for ensuring that follow-up includes any supplemental investigations as indicated to elucidate the nature and/or causality. Further information on follow-up procedures is provided in Section 10.4 (Appendix 4).

8.3.1. Timing and Mechanism for Collecting Events

The following table describes the timing, deadlines, and mechanism for collecting events.

Event	Collection Start	Collection Stop	Timing for Reporting to Sponsor or Designee	Mechanism for Reporting	Back-Up Method of Reporting
Adverse Event					
AE	Signing of the ICF	Participation in study has ended	As soon as possible upon site awareness	AE eCRF	N/A

Event	Collection Start	Collection Stop	Timing for Reporting to Sponsor or Designee	Mechanism for Reporting	Back-Up Method of Reporting
Serious Adverse Event					
SAE and SAE updates – prior to start of study intervention and deemed reasonably possibly related with study procedures	Signing of the ICF	Start of intervention	Within 24 hours of awareness	SAE eCRF	SAE paper form
SAE* and SAE updates – after start of study intervention	Start of intervention	Participation in study has ended	Within 24 hours of awareness	SAE eCRF	SAE paper form
SAE* – after participant’s study participation has ended and the investigator becomes aware	After participant’s study participation has ended	N/A	Promptly	SAE paper form	N/A

Event	Collection Start	Collection Stop	Timing for Reporting to Sponsor or Designee	Mechanism for Reporting	Back-Up Method of Reporting
Pregnancy					
Pregnancy in female participants and female partners of male participants	After the start of study intervention	2 months after last injection for female participants and 4 months after last injection for female partners of male participants	Within 24 hours of learning of the pregnancy	SAE eCRF	SAE paper form
Product Complaints					
PC associated with an SAE or might have led to an SAE	Start of study intervention	End of study intervention	Within 24 hours of awareness	Product complaint form	N/A
PC not associated with an SAE	Start of study intervention	End of study intervention	Within 1 business day of awareness	Product complaint form	N/A
Updated PC information	—	—	As soon as possible upon site awareness	Originally completed product complaint form with all changes signed and dated by the investigator	N/A

Event	Collection Start	Collection Stop	Timing for Reporting to Sponsor or Designee	Mechanism for Reporting	Back-Up Method of Reporting
PC (after participant's study participation has ended and the investigator becomes aware)	After participant's study participation has ended	N/A	Promptly	Product complaint form	N/A

Abbreviations: AE = adverse event; eCRF = electronic case report form; N/A = not applicable; PC = product complaint; SAE = serious adverse events.

*Serious adverse events, including death, caused by disease progression should not be reported unless the investigator deems them to be possibly related to study treatment.

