2.2. Background

Obesity is a chronic disease, and its increasing prevalence is a public health concern associated with rising incidence of T2D, increased risk for premature death, and increased risk for some cancers (AMA 2013; Council on Science and Public Health 2013; Lauby-Secretan et al. 2016). There remains an unmet need in the pharmacologic treatment of obesity for drugs that are safe, efficacious, and well tolerated.

Structure of LY3437943

LY3437943 is a novel synthetic peptide, which shows potent agonist action at GIP, GLP-1, and Gcg receptors (GIPR, GLP-1R, and GcgR, respectively). It includes a linear peptide component of 39 amino acid residues conjugated to a C20 fatty acid moiety.

Nonclinical data with efficacy and toxicology

In nonclinical pharmacology models, LY3437943 demonstrated a greater effect on glucose-dependent insulin secretion compared with an existing GLP-1RA, as demonstrated by intravenous glucose tolerance test in rats and with greater weight loss in DIO mice. The body weight reduction in DIO mice was primarily due to loss of fat mass and was associated with lowered total plasma cholesterol and reduced liver fat content.

The nonclinical safety profile of LY3437943 was evaluated in a single-dose cardiovascular safety pharmacology study in monkeys, 13-week and 6-month repeat-dose toxicology studies in rats and monkeys, a female fertility study in rats, embryo-fetal development studies in rats and rabbits, an in vitro human Ether-a-go-go-Related Gene (hERG) assay, and an in vivo micronucleus genotoxicity study in rats. Findings in all studies were consistent with, or secondary to, LY3437943-related pharmacology, and included body weight loss and/or decreased body weight gain, and decreased food consumption. Additional findings in monkeys included changes in cardiovascular parameters attributed to on-target GIP, GLP-1, and/or Gcg pharmacology. **CCI**

Summary of clinical studies

Study J1I-MC-GZBA (GZBA) was a first-in-human, single-ascending dose study investigating the safety, tolerability, and pharmacokinetic/pharmacodynamic (PK/PD) of LY3437943 administered as a SC injection in 45 healthy participants.

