8.3.2.5. Deaths

All deaths will be adjudicated by a committee of physicians external to Lilly. This committee will be blinded to treatment assignment.

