10.1.4 Committees Structure

An independent CEC will be formed to adjudicate major adverse cardiovascular events, deaths, and pancreatitis AEs, as specified in Section [8.3.2](#).

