10.1.8 Study and Site Start and Closure

10.1.8.1 Discontinuation of the Study

The sponsor designee reserves the right to terminate the study at any time for any reason at the sole discretion of the sponsor. The study will be discontinued if Lilly or its designee judges it necessary for medical, safety, regulatory, or other reasons consistent with applicable laws, regulations, and GCP.

Medical Oversight and Safety Review

Ongoing safety review(s) by designated sponsor personnel will occur and be documented. Such reviews will include

- monitoring and assessing the safety information collected during the trial both in real time and periodically
- reviewing safety data for trends that need action, and
- detecting adverse drug/device effects.

A safety investigation will be triggered to determine if the study should be terminated early based on the following criteria

- two study participants develop the same TEAE or SAE considered possibly or probably related to study drug that is severe or medically significant but not immediately life-threatening; or where hospitalization or prolongation of hospitalization is indicated; or is disabling; or limits self-care activities of daily living
- one study participant develops any TEAE or SAE regardless of attribution to study drug that has life-threatening consequences or requires urgent intervention
- death of any study participant at any time, and
- any other clinically significant safety signal.

If the study is prematurely terminated or suspended, the sponsor shall promptly inform the investigators, the IECs/IRBs, the regulatory authorities, and any contract research organization(s) used in the study of the reason for termination or suspension, as specified by the applicable regulatory requirements. The investigator shall promptly inform the participant and assures appropriate participant therapy and/or follow-up.

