10.4.2 Definition of SAE

If an event is not an AE per definition above, then it cannot be an SAE even if serious conditions are met (for example, hospitalization for signs/symptoms of the disease under study, death due to progression of disease).

SAE is defined as any untoward medical occurrence that, at any dose:**a. Results in death****b. Is life-threatening**

The term "life-threatening" in the definition of "serious" refers to an event in which the participant was at risk of death at the time of the event. It does not refer to an event, which hypothetically might have caused death, if it were more severe.

c. Requires inpatient hospitalization or prolongation of existing hospitalization

- In general, hospitalization signifies that the participant has been admitted to hospital for observation and/or treatment that would not have been appropriate in the physician's office or outpatient setting. Complications that occur during hospitalization are AEs. If a complication prolongs hospitalization or fulfills any other serious criteria, the event is serious. When in doubt as to whether "hospitalization" occurred or was necessary, the AE should be considered serious.
- Hospitalization for elective treatment of a preexisting condition that did not worsen from baseline is not considered an AE.

d. Results in persistent disability/incapacity

- The term disability means a substantial disruption of a person's ability to conduct normal life functions.

 • This definition is not intended to include experiences of relatively minor medical significance, such as uncomplicated headache, nausea, vomiting, diarrhea, influenza, and accidental trauma (for example, sprained ankle) which may interfere with or prevent everyday life functions but do not constitute a substantial disruption.

e. Is a congenital anomaly/birth defect
 
 • Abnormal pregnancy outcomes (for example, spontaneous abortion, fetal death, stillbirth, congenital anomalies, and ectopic pregnancy) are considered SAEs.

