4.6.7.10. Major Adverse Cardiovascular Events

Major adverse cardiovascular events reported by investigators are adjudicated by an independent CEC in a blinded fashion.

The CV AEs to be adjudicated include deaths due to CV cause, myocardial infarction, hospitalization for unstable angina, hospitalization for heart failure, coronary interventions (such as coronary artery bypass graft or percutaneous coronary intervention); and cerebrovascular events, including cerebrovascular accident (stroke) and transient ischemic attack.

Only adjudicated MACE will be considered as AESI. The counts and percentages of participants with adjudicated MACE may be summarized by treatment.

In addition, MACE reported by investigator may also be summarized although a MACE reported by investigator is not considered as AESI.

A listing of participants reporting MACE events, either reported by investigator or identified by the CEC, will be provided. The listing will include treatment, participants identification including the site number, date of event, type of event as reported by the investigator, type of event as adjudicated by the CEC, time from first dose of study drug to the event, and time from last dose to the event (if participant has discontinued study drug prior to the event).

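### Protocol 8.3.1 exempts SAEs, including deaths, attributed to an undefined disease progression from reporting unless judged possibly drug-related, in conflict with the rules that every death is adjudicated and triggers a safety investigation

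*Protocol*

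**What the plan says.** Three places narrow what sites report.

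- **Protocol 8.3.1, table footnote.** SAEs, deaths included, "caused by disease progression should not be reported unless the investigator deems them to be possibly related to study treatment". The asterisk stands on two rows: SAEs after the start of intervention (24-hour reporting) and SAEs learned of after participation has ended (prompt reporting). The AE row and the pre-intervention SAE row do not carry it.
- **Protocol 10.4.1.** The disease under study and its expected progression are not AEs, unless more severe than expected for that participant.
- **Protocol 10.4.2.** An event that is not an AE cannot be an SAE even if it meets a seriousness condition. The examples are "hospitalization for signs/symptoms of the disease under study, death due to progression of disease".

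Other places need the events without a filter on cause.

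- **Protocol 8.3.2.5:** "All deaths will be adjudicated by a committee of physicians external to Lilly". Section 8.3.2 lists deaths, pancreatitis and major adverse cardiovascular events as adjudicated events of special interest, and 10.1.4 gives the committee the same remit: "An independent CEC will be formed to adjudicate major adverse cardiovascular events, deaths, and pancreatitis AEs".
- **Protocol 8.3.2.4** lists the nonfatal cardiovascular events to be adjudicated, among them hospitalization for heart failure and for unstable angina.
- **Protocol 10.1.8.1** starts a safety investigation, which decides whether to stop the study early, on "death of any study participant at any time". A life-threatening TEAE or SAE in one participant also starts it, whatever its attribution.

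The SAP describes how cardiovascular events reach the committee (4.6.7.10): "Major adverse cardiovascular events reported by investigators are adjudicated by an independent CEC in a blinded fashion".

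**The concern.** The footnote makes reporting depend on two investigator judgements: that the event was caused by disease progression, and that it was not possibly drug-related. The first has no definition in this trial. Obesity does not progress in a sense that sites would share, and the population invites differing views. Protocol 2.2 says obesity is associated with "increased risk for premature death, and increased risk for some cancers". Inclusion criterion 2 names hypertension, dyslipidemia and cardiovascular disease, including Class I-II heart failure, as weight-related comorbidities. Participants may be as old as 75.

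Safety and tolerability is a stated secondary objective. Phase 1 showed dose-dependent heart-rate increases (2.2). There is no data monitoring committee (9.6), and the study team's periodic review is blinded (8.2.5). The sponsor also plans an aggregate assessment of SAEs expected in this population independent of drug exposure (2.3) and summaries of deaths and other cardiovascular endpoints (9.4.4.2). All of this presupposes that the events are reported first and attributed afterwards. The placebo arm is included partly to show whether safety effects differ from no treatment (4.2), so events unrelated to the drug can be separated by comparison after capture.

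**Working it through.** No arithmetic applies. The check is to follow three events through the text. In each, the investigator attributes the event to progression and does not think it possibly drug-related.

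| Event | Under the exemption | What another section needs |
|---|---|---|
| Death | 8.3.1: no SAE report. 10.4.2: not an SAE if it is not an AE | 8.3.2, 8.3.2.5, 10.1.4: adjudication. 10.1.8.1: safety investigation |
| Hospitalization for heart failure | 8.3.1: no SAE report. 10.4.2: hospitalization for the disease under study is an example of a non-SAE | 8.3.2.4: adjudication |
| Life-threatening event | 8.3.1: no SAE report. 10.4.1: possibly not an AE | 10.1.8.1: safety investigation whatever the attribution |

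1. **Does the relatedness exception resolve the conflict?** No. It restores reporting only when the drug is suspected. Adjudication of deaths and the any-death trigger do not depend on causality.

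2. **Do the AE definitions resolve it?** Only in part. Section 10.4.1 counts new conditions and exacerbations of pre-existing ones as AEs, and its progression exclusion has the more-severe-than-expected limit. But the footnote acts on events that are already SAEs, so meeting the AE and SAE definitions does not take an event outside it. Section 8.3.1.1, which sends serious AEs to SAE reporting, leaves the footnote in place.

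3. **Does the life-threatening trigger stand by itself?** Not fully. It is worded for TEAEs and SAEs, so an event that 10.4.1 excludes from the AE definition falls outside it.

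4. **Are there other routes to the sponsor?** Several, each partial:
   - The AE row in 8.3.1 has no asterisk, but its timing is as soon as possible, and it covers only what counts as an AE.
   - Protocol 10.4.4 requires a copy of post-mortem findings for a participant who dies. It gives no deadline and does not cover nonfatal events.
   - SAP 4.1 uses date of death to end participation, and SAP 4.6.3 requires a narrative for each death and SAE. Both are analysis and reporting steps.
   - SAP 4.6.7.10 lists events identified by the committee as well as those reported by investigators, but does not say how the committee would find an event that was not sent to it.

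   None of these carries the 24-hour deadline that 8.3.1 sets for SAEs during the study.

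**The case against.** The strongest reply is that a sensible site would report anyway. The rules on events of special interest in 8.3.2 are specific, carry no causality filter and tell sites to collect additional data; a general table footnote should yield to them. A new infarction or stroke is a new condition under 10.4.1, invasive or malignant cancers are named in 10.4.2 as examples of events usually considered serious, and the routes above would probably bring most deaths to the sponsor's attention. The sponsor also plans real-time and periodic safety review (10.1.8.1).

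Much of this stands, and it limits the finding. It does not remove the conflict. No text says that 8.3.2 overrides the footnote, and the footnote names death expressly.

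A reader might go further in three ways that the documents do not support:

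- **That an unreported event can never reach the committee.** SAP 4.6.7.10 allows for events identified by the committee, and deaths have the back-up routes listed above.
- **That the protocol treats premature death as part of the course of obesity.** It states an association with increased risk, not that such deaths are progression.
- **That a given share of the safety evidence would be lost.** The documents give no rate for deaths or cardiovascular events and nothing on how often sites would use the exemption. Any such figure would rest on assumptions only.

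**Conclusion.** The conflict is real and stands in current text. A site cannot apply the 8.3.1 footnote to a death and also supply what 8.3.2.5 and 10.1.8.1 require. The exposure covers deaths, the events in 8.3.2.4 and life-threatening events during and after treatment. It is reduced, but not closed, by routes without a 24-hour deadline. Its size cannot be quantified from the documents. The conclusion assumes that sites treat the footnote as operative and that at least some would attribute a weight-related event to progression, a term left undefined. It does not assume that such events will be common. This should be corrected because the remedy is cheap and any-death review is one of the plan's few stated safety triggers.

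**What to change.** Make three linked wording changes.

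1. In 8.3.1, delete the footnote and both asterisks, or state that it does not apply to deaths and to adjudicated events of special interest.
2. State that the progression exclusion in 10.4.1 and the examples in 10.4.2 do not apply to these events. Amending 8.3.1 alone would leave the exclusion in the AE definition, on which 10.4.2 depends.
3. State that all deaths and all events listed in 8.3.2.4 are reported to the sponsor and sent to the committee whatever the presumed cause, with SAE classification still decided by the 10.4.2 seriousness criteria. Those that qualify as SAEs during the study then fall under the existing 24-hour rule.

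A reader might infer that every 8.3.2.4 event should simply be made an SAE. That would create new contradictions. Section 10.4.4 makes an event serious only when it meets a predefined outcome, 10.4.1 treats the underlying condition and not the procedure as the AE, and 10.4.2 excludes elective hospitalization for an unworsened pre-existing condition. The list in 8.3.2.4 includes coronary interventions and transient ischemic attack, which need not meet those tests.

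The cost is a wording amendment and possibly a few extra reports.

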8.3.1.1. Adverse Event Monitoring with a Systematic Questionnaire

Nonleading AE collection should occur prior to the collection of the C-SSRS.

If a suicide-related event is discovered during the C-SSRS but was not captured during the nonleading AE collection, sites should not change the AE form.

If an AE is serious or leads to discontinuation, it needs to be included on the AE form and the process for reporting SAEs is followed.

8.3.2. Adverse Events of Special Interest

The following are adverse events of special interest and will be adjudicated by an independent clinical endpoint committee (CEC):

- pancreatitis
- major adverse cardiovascular events, and
- deaths.

The following are additional adverse events of special interest for this program that will not be adjudicated by an external committee:

- hypoglycemia (Level 2 and 3)
- thyroid malignancies and C-cell hyperplasia
- supraventricular arrhythmias and cardiac conductive disorders
- hypersensitivity events
- injection site reactions

- hepatobiliary disorders
- severe GI AEs
- antidrug antibodies
- acute renal events, and
- depression, suicidal ideation or behavior monitoring.

Sites should collect additional details and data regarding these safety topics, as instructed on the applicable eCRFs, and detailed below.

